4.5.2. Laboratory Safety Variables

Hematology, chemistry, urinalysis, and pregnancy testing samples will be analyzed by a central laboratory.

Samples for laboratory testing will be collected according to visit schedule ([Appendix 10.2](#)). Tests will include

Serum Chemistry

Sodium	Total protein, serum	Total bilirubin ¹
Potassium	Creatinine	Total cholesterol ²
Chloride	Blood urea nitrogen (BUN)	Triglycerides
Carbon dioxide	AST	Uric acid
Calcium	ALT	CPK ³
Glucose	Alkaline phosphatase	
Albumin	Lactate dehydrogenase (LDH)	

- 1 Direct and indirect bilirubin will be measured when the total bilirubin is above the ULN
- 2 Low-density lipoprotein and high-density lipoprotein
- 3 CPK isoenzymes will be measured when CPK >5× the ULN

Hematology

Hemoglobin	Differential:
Hematocrit	Neutrophils
Red blood cells (RBCs)	Lymphocytes
White blood cells (WBCs)	Monocytes
Red cell indices	Basophils
Platelet count	Eosinophils

Urinalysis

Color	Glucose	RBC
Clarity	Blood	Hyaline and other casts
pH	Bilirubin	Bacteria
Specific gravity	Leukocyte esterase	Epithelial cells
Ketones	Nitrite	Crystals
Protein	WBC	Yeast

Other Laboratory Tests

Serum and urine pregnancy testing will be performed for all female patients of childbearing potential at time points according to [Appendix 10.2](#). The following tests will be performed at screening: HIV, HBsAg, HBsAb, HBcAb, hepatitis C antibody, tuberculosis (will be performed on a country-by-country basis according to local guidelines if required by regulatory authorities or ethics boards).

4.5.3. Vital Sign Variables

The following vital signs parameters will be collected:

- Respiratory rate (bpm)
- Heart rate (beats/min)
- Sitting systolic and diastolic blood pressures (mmHg)
- Body temperature (°C)

Vital signs including temperature, sitting blood pressure, heart rate, and respiration, will be collected predose at every in-clinic visit. At the first 3 administrations of study drug (day 1, week 2, and week 4 for patients receiving Q2W treatment and day 1, week 4, and week 8 for patients receiving Q4W treatment), sitting blood pressure, heart rate, and respiratory rate will also be assessed at 30 (±10) minutes postdose and then at 2 hours (±15 minutes). See [Appendix 10.2](#) for assessment time points.

4.5.4. Body Weight and Height

Body weight and height will be measured at time points according to [Appendix 10.2](#).

4.5.5. Physical Examination Variables

The physical examination variable values are dichotomized to normal and abnormal. A thorough and complete physical examination will be performed at time points according to visit schedule ([Appendix 10.2](#)).

4.5.6. 12-Lead Electrocardiography (ECG) Variables

Standard 12-Lead ECG parameters include: Ventricular HR, PR interval, QRS interval, corrected QT interval (QTc Fridericia [QTcF] =QT/[RR^{0.33}] and QTc Bazett [QTcB]=QT/[RR^{0.5}]) ECG status: normal, abnormal not clinical significant or abnormal clinical significant. See [Appendix 10.2](#) for assessment time points.

4.6. Pharmacokinetic (PK) Variables

Serum samples for measuring functional dupilumab concentrations will be collected at time points according to [Appendix 10.2](#) . PK parameters may include, but are not limited to C_{trough} and $C_{\text{trough,SS}}$.

4.7. Immunogenicity Variables

The immunogenicity variables are ADA status, titer, NAb status and time-point/visit. Serum samples for anti-dupilumab antibody will be collected at time points according to visit schedule ([Appendix 10.2](#)). ADA analysis will be conducted on samples collected at baseline, EOT and EOS. ADA sample at Week 4 will only be analyzed for ADA in patients positive for ADA in a later visit such as EOT or EOS.

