Positive anti-drug antibody (ADA) was observed in 50 patients (64.9 %) at any time, 31 of which (40.3% out of total) were categorized as persistent treatment-emergent ADA. The rate of occurrence of persistent ADA were similar across cohorts with a trend of higher rates in the adolescents compared with school-going children. Six patients (12.0%) had high titers ( $> 10,000$ ), 4 from the 2 mg/kg groups and 2 from 4 mg/kg groups. Within each age group, there also seemed to be a trend for higher incidence of persistent ADA in lower dose cohorts as compared to higher dose cohorts. Dupilumab concentrations in patients with high titers were markedly reduced compared to those with a negative response, or low or moderate titers. These patients had an inferior clinical response to the study drug as compared to the overall study population. The high titer ADAs were not associated with any systemic symptoms of hypersensitivity in these patients, although one of these patients did experience an injection site reaction, which was mild in intensity.

Standard safety monitoring used in previous trials with dupilumab is planned to be conducted during this study. An internal safety monitoring team will be reviewing blinded data at regular intervals during the study to monitor the safety of patients. An Independent Data Monitoring Committee (IDMC) overseeing the entire dupilumab clinical development will be in place for the duration of the study to monitor the safety of the patients and to provide the sponsor with appropriate recommendations in due time to ensure the safety of the patients.

Additional information can be found in the Investigator's Brochure.

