#### 4.4. Anti-Drug Antibody Variables

Anti-drug (dupilumab) antibody variables include status (positive or negative) and titer as follows:

- Total number of patients negative in ADA assay at all time
- Total number of patients positive in ADA assay at any time
- Total number of patients with preexisting immunoreactivity – defined as either an ADA positive response in the assay at baseline with all post-baseline ADA results negative, or a positive response at baseline with all post-baseline ADA titer  $< 4$ -fold over baseline titer level

- Total number of patients with treatment-emergent ADA response in ADA assay – defined as a positive response in the ADA assay post-first dose, when baseline results are negative, or missing. The treatment-emergent responses will be further characterized into the following categories:
  - Persistent ADA response – a treatment-emergent ADA positive response with 2 or more consecutive positives in the ADA assay separated by greater than a 12-week period, with no ADA negative samples in between
  - Transient ADA response – a treatment-emergent ADA positive response that is not considered persistent or indeterminate
  - Indeterminate ADA response – a treatment-emergent ADA positive response with only the last collected sample positive in the ADA assay
- Total number of patients with a treatment-boosted response – defined as a positive response in the ADA assay post first dose that is  $\geq 4$ -fold over baseline titer levels when baseline results are positive
- Titer value category
  - Low (titer  $< 1,000$ )
  - Moderate ( $1,000 \leq \text{titer} \leq 10,000$ )
  - High (titer  $> 10,000$ )

Anti-drug antibody positive samples will be further characterized for the presence of neutralizing antibody (NAb) response:

- Total number of patients positive in the NAb assay at the time points analyzed.

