5.10. Analysis of Immunogenicity Data

5.10.1. Analysis of ADA Data

The immunogenicity variables described in Section 4.7 will be summarized using descriptive statistics in the ADA analysis set. Frequency tables of the proportion of patients with pre-existing immunoreactivity, treatment-emergent, treatment-boosted, persistent ADA responses, and titer categories will be presented as absolute occurrence (n) and percent of patients (%) by treatment groups.

ADA response categories and titer categories are defined as follows:

- Pre-existing immunoreactivity, defined as either an ADA positive response in the assay at baseline with all post first dose ADA results negative, OR a positive response at baseline with all post first dose ADA responses less than 4-fold over baseline titer levels
- Treatment-emergent response, defined as a positive response in the ADA assay post first dose when baseline results are negative or missing. The treatment-emergent responses will be further characterized as Persistent, Indeterminate or Transient
 - Persistent Response - Treatment emergent ADA positive response with two or more consecutive ADA positive sampling time points separated by greater than 12-week period, with no ADA negative samples in between
 - Indeterminate Response - as a treatment-emergent response with only the last collected sample positive in the ADA assay
 - Transient Response - a treatment emergent ADA positive assay response that is not considered persistent or indeterminate.
- Treatment-boosted response, defined as a positive response in the ADA assay post first dose that is greater than or equal to 4-fold over baseline titer levels, when baseline results are positive
- Maximum Titer Values (Titer value category)
 - Low (titer <1,000)
 - Moderate ($1,000 \leq \text{titer} \leq 10,000$)
 - High (titer >10,000)

The following summaries will be provided based on AAS:

- Number (%) of ADA-negative patients
- Number (%) of patients with pre-existing immunoreactivity by treatment group and ADA titer categories
- Number (%) of treatment-emergent ADA-positive patients by treatment group and ADA titer categories
 - Number (%) of persistent treatment-emergent ADA-positive patients

- Number (%) of indeterminate treatment-emergent ADA-positive patients
- Number (%) of transient treatment-emergent ADA-positive patients
- Number (%) of treatment-boosted ADA-positive patients

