5.11.2. Immunogenicity on Safety and Efficacy

Association between ADA response categories and safety events will focus on the following events:

- Hypersensitivity (SMQ: Hypersensitivity [Narrow])
- Anaphylaxis (SMQ: Anaphylaxis [Narrow])

Number (%) of patients with the above mentioned safety events will be summarized by treatment-emergent, treatment-boosted, persistent ADA response status, and neutralizing antibody status during the TEAE period.

Association between ADA and the primary and key secondary efficacy endpoints may be explored and summarized in SAF using individual patient spaghetti plots.

The safety and efficacy analyses mentioned above will be conducted using the following ADA response categories:

- ADA positive patients, that is patients with treatment-emergent or treatment-boosted response
- ADA negative patients, that is patients with pre-existing immunoreactivity or negative in the ADA assay at all time points
- Patients with persistent ADA response

- NAb positive patients, that is patients who were positive in the NAb assay at any time point analyzed.
- Maximum post-baseline titer level in treatment-emergent or treatment-boosted ADA positive patients:
 - High,
 - Moderate,
 - Low

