8. The type, amount, and potency of topical products used during the study will be recorded. The amount of TCS used will be determined by weighing the tube at each visit through the end of the study.
9. Assessments/procedures should be conducted in the following order: patient reported outcomes (other than patient assessment of injection pain), investigator assessments, safety and laboratory assessments (including sample collection for ADA, PK, biomarker, [REDACTED]), administration of study drug, and assessment of injection pain.
10. The questionnaires will be administered only to the subset of patients or parents/caregivers who speak fluently the language in which the questionnaire is presented (based on availability of validated translations in participating countries).
11. Refer to protocol Section 8.2.2 for details on who (parent or caregiver) is required to complete the specific questionnaires.

12. DFI is to be completed by parent/caregiver.
13. Injection pain assessment at week 2 will only be performed for patients on Q2W treatment
14. Samples will be collected before the injection of study drug
15. TB testing will be performed on a country-by-country basis, according to local guidelines if required by regulatory authorities or ethics boards.
16. Urine pregnancy testing at week 2 will only be performed for patients who receive Q2W treatment.
17. EOT is end of study for patients who enter the OLE.
18. Patients who experience adverse events of special interest related to eye disorders (refer to Protocol Section 9.4.3) will also be referred to an ophthalmologist (preferably with expertise in treating pediatric patients or Cornea and External Eye Disease [‘front-of-the-eye’] subspecialty expert). Further evaluation of these AESIs will be performed including any additional tests, if applicable, as per the discretion of the ophthalmologist.

Footnotes for Schedule of Events Table 2

1. Starting at visit 4, study drug will be dispensed to the parents (or caregivers) for the dose that will be administered before the next clinic visit. Parents (or caregivers) will return the study kit box (for prefilled syringes) at each subsequent in-clinic visit. At these in-clinic visits, sites will perform accountability assessment for the study drug that the parents (or caregivers) have returned to the site.

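### SAP 4.7 leaves the Week 4 ADA sample unassayed unless a later sample is positive, so a child positive only at Week 4 is counted as ADA negative and the any-time and transient counts are understated

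*SAP*

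**What the plan says.** **Samples drawn.** The schedules of events (Protocol 8.1, SAP 10.2) collect ADA samples at baseline (D1), Week 4 (D29) and Week 16 (D113). They add Week 28 (D197) for children who do not enter the OLE, and early-termination and unscheduled visits. For the others, "EOT is end of study for patients who enter the OLE".

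**Samples assayed.** SAP 4.7 says "ADA analysis will be conducted on samples collected at baseline, EOT and EOS". It then adds that the "ADA sample at Week 4 will only be analyzed for ADA in patients positive for ADA in a later visit", with EOT and EOS given as examples of that later visit.

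**Results to be reported.** Protocol 4.4 lists "Total number of patients positive in ADA assay at any time" and "Total number of patients negative in ADA assay at all time", and Protocol 10.5.5 says that the variables in 4.4 will be summarised. SAP 5.10.1 plans counts of ADA-negative, persistent, indeterminate and transient patients. It defines the last as a residual: "Transient Response - a treatment emergent ADA positive assay response that is not considered persistent or indeterminate". SAP 5.11.2 tabulates hypersensitivity and anaphylaxis by ADA category, and its reference group is "ADA negative patients, that is patients with pre-existing immunoreactivity or negative in the ADA assay at all time points".

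SAP 1.2.3 records no modification from the protocol's statistical section.

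**The concern.** The reporting labels cover all time points, but the assay rule does not. Week 4 is the only scheduled post-baseline ADA draw before Week 16, and it is tested only in children already known to be positive later. A response seen only at Week 4 therefore drops out of the count without being looked for. The error runs in one direction: positives can be lost and none can be gained.

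Two outputs are affected. One is the ADA incidence table. The other is the comparison in SAP 5.11.2. Protocol 7.1 monitors children on site after the first three doses, which run to Week 4 on Q2W and Week 8 on Q4W. A child with an early antibody response and an early reaction could be placed among the ADA negatives, which would pull the comparison toward no association. Antibody status is not incidental here. Protocol 3.2.3 reports markedly reduced concentrations and inferior response at high titre, and Protocol 3.2.4.2 links serum sickness in adults to high titres.

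**Working it through.** The plan states no figure to reproduce on this point. The check classifies every possible post-dose pattern for a baseline-negative child, first with all samples assayed and then under SAP 4.7.

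**Inputs.** Visit days are D29, D113 and D197 (schedules of events). The definitions come from SAP 5.10.1: persistent needs consecutive positives more than 12 weeks (84 days) apart with no negative between; indeterminate means only the last sample is positive; transient is any other treatment-emergent response.

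**Spacing.** Week 4 to Week 16: 113 − 29 = 84 days. Week 16 to Week 28: 197 − 113 = 84 days. Both are exactly 12 weeks, so on nominal days a single such gap does not exceed 12 weeks. With the ±3-day windows, the first gap runs from (113 − 3) − (29 + 3) = 78 to (113 + 3) − (29 − 3) = 90 days.

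**OLE entrants (2² = 4 patterns)**

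| W4 | W16 | All assayed | SAP 4.7 |
|---|---|---|---|
| − | − | negative | negative |
| − | + | indeterminate | indeterminate |
| + | − | transient | **negative** |
| + | + | transient* | transient* |

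**Children followed to Week 28 (2³ = 8 patterns)**

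| W4 | W16 | W28 | All assayed | SAP 4.7 |
|---|---|---|---|---|
| − | − | − | negative | negative |
| − | − | + | indeterminate | indeterminate |
| − | + | − | transient | transient |
| − | + | + | transient* | transient* |
| + | − | − | transient | **negative** |
| + | − | + | transient | transient |
| + | + | − | transient* | transient* |
| + | + | + | persistent | persistent |

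*On nominal days under the literal rule of more than 12 weeks; persistent if a gap of exactly 84 days is taken to qualify.

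**Result.** Two of the 12 patterns change class, W4+/W16− and W4+/W16−/W28−. Both move from transient to negative. The other ten are unchanged, and this holds whether the cut is above 84 days or at least 84 days.

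**Two side effects.** In a baseline-positive child, a boosted response seen only at Week 4 would be labelled pre-existing immunoreactivity, which SAP 5.11.2 also groups with ADA negative. A child whose only post-dose sample is Week 4 has no assayed post-dose result and so falls outside the ADA set (SAP 3.4).

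**Scale.** Two dupilumab groups of 110 (SAP 2.2) make 220 patients. The Week 4-only rate is not given. Assumed at 5%: 0.05 × 220 = 11. Assumed at 10%: 0.10 × 220 = 22.

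**The case against.** The strongest reply is that the rule is openly pre-specified. The protocol says that samples are collected and variables summarised, not that every sample is assayed. SAP 5.11.2 is descriptive. All hypersensitivity and anaphylaxis events are still reported in the safety set whatever the ADA status. The rule also keeps the information needed to separate persistent from indeterminate responses in later positives. All of this is correct and limits the consequence. It does not make labels that claim all time points true when one scheduled time point is untested.

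Early-termination and unscheduled samples could help. The trigger in SAP 4.7 is not confined to EOT and EOS, and SAP 6.4 lets ADA values from such visits be summarised. A positive there could prompt the Week 4 assay. SAP 4.7 does not say that those samples are assayed, so this is a possible mitigation and not a stated one.

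A reader might infer three stronger claims that the documents do not support.

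- **Transient results cannot be obtained.** They can: W4−/W16+/W28−, W4+/W16−/W28+ and, under the literal spacing rule, W4+/W16+ pairs 84 days or less apart all yield transient. For OLE entrants, only a resolved response is out of reach.
- **Every response that has cleared by Week 16 is reported as negative.** One that is positive again at Week 28 triggers the Week 4 assay.
- **The earlier paediatric study gives the size.** Protocol 3.2.3 reports "Positive anti-drug antibody (ADA) was observed in 50 patients (64.9 %) at any time", 31 of them persistent. The remainder is 50 − 31 = 19, or 19/77 = 24.7% (77 is the denominator that reproduces 64.9%). By the definitions in Protocol 4.4, that remainder can mix pre-existing, boosted, indeterminate and transient responses. The regimen was a single dose followed by four weekly mg/kg doses. No share of the 19 can be assigned to Week 4 alone.

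**Conclusion.** The concern holds in this form. Followed exactly, SAP 4.7 counts a baseline-negative child who is positive at Week 4 and negative in every later assayed sample as ADA negative. The any-time count is a lower bound, the transient count is understated, and the count negative at all time points is an upper bound. A resolved response cannot be detected at scheduled visits in OLE entrants, and the ADA-negative group in SAP 5.11.2 may contain early responders.

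The size is unknown. The 11 to 22 children out of 220 rest wholly on an assumed Week 4-only rate of 5% to 10% and are not a forecast. The primary and other efficacy analyses in the testing hierarchy are unaffected. This is a mislabelled safety output with a known direction of error, and it should be corrected.

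**What to change.** **Relabel (cheapest).** In SAP 5.10.1 and 5.11.2, report ADA status at Week 16/EOS. For example, use *not positive at Week 16/EOS* in place of a label that claims all time points. State that Week 4-only responses are not captured. List the departure from Protocol 4.4 and 10.5.5 in SAP 1.2.3. This costs SAP wording and a less complete ADA statement.

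**Or assay.** Test the Week 4 sample already collected from all patients in the ADA set. This needs no extra blood or visit and lets the current labels stand as regards Week 4. The cost is at most about 330 further assays, less those already triggered by a later positive, plus titre and neutralising-antibody work on any new positives.

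Under either option, SAP 4.7 should say whether early-termination and unscheduled samples are assayed and whether a positive there triggers the Week 4 assay.

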4.8. Biomarkers Variables

Biomarkers to be analyzed in this study are:

- TARC
- Total serum IgE
- Immunoglobulin profiling
- Lactate dehydrogenase (LDH) [which will be measured as part of the blood chemistry]

Serum samples for measurements of biomarkers to study the PD activity of dupilumab in pediatric AD patients will be collected at time points according to [Appendix 10.2](#) .

5. STATISTICAL METHODS

For continuous variables, descriptive statistics will include the following: the number of patients reflected in the calculation (n), mean, median, standard deviation, first quartile (Q1), third quartile (Q3), minimum, and maximum.

For categorical or ordinal data, frequencies and percentages will be displayed for each category.

All data will be summarized by 3 treatment groups (i.e. dupilumab q2w dose, dupilumab q4w dose and placebo).

5.1. Demographics and Baseline Characteristics

Demographics and baseline characteristics will be summarized by treatment group for FAS. Listing of demographics and baseline characteristics will be presented.

5.2. Medical and AD History

Medical history will be summarized by primary SOC and PT for each treatment group. The table will be sorted by decreasing frequency of SOC followed by PT based on the overall incidence across treatment groups. Medical history will be listed.

Information on conditions related to AD includes diagnosis of AD and AD treatment history, asthma, allergic conjunctivitis, allergic rhinitis, chronic rhinosinusitis, nasal polyps, eosinophilic esophagitis, food allergy hives and other allergies due to medications, animals, plants, mold, dust mites, etc. will be summarized.

5.3. Pre-treatment/Concomitant Medications/Procedures

Number and proportion of patients taking prior/concomitant medications, prohibited medications and rescue medications will be summarized, sorted by decreasing frequency of ATC Level 2 and ATC level 4, based on the overall incidence for the combined dupilumab treatment groups. Patients will be counted only once for each medication class (ATC level 2 and 4) linked to the medication.

Number and proportion of patients taking prior/concomitant procedures, prohibited procedures and rescue procedures will be summarized, sorted by decreasing frequency of SOC and PT based on the overall incidence for the combined dupilumab treatment groups. Patients will be counted only once for each SOC and PT linked to the procedure.

Prior medications or procedures started before screening visit and started between screening visit and first injection date will be summarized separately.

Number and proportion of patients taking adjudicated rescue treatment (concomitant topical treatments (high potency TCS/TCI), systemic immune-suppressants) and other treatments (emollients/ antihistamines) will also be summarized separately.

Kaplan Meier curves for time to first rescue use will be generated.

The compliance of moisturizers (emollients) used from 7 days before the baseline visit to end of study, which is defined as the (number of days moisturizers used during the period) / (number of days within the period) x 100%, will be summarized by treatment group

Listing of medications and procedures will be provided.

